## 5.1.2. Safety and Tolerability

Please refer to the Investigator's Brochure for a detailed discussion of safety findings for studies in healthy subjects, cancer, CKD, and PH patients with bardoxolone methyl.

#### 5.1.2.1. Fluid Overload

Similar to endothelin receptor antagonists (ERAs) in certain patient populations, including bosentan in advanced congestive heart failure and avosentan in advanced CKD, bardoxolone methyl treatment was found to be associated with an increased risk for fluid overload and heart failure hospitalizations in the BEACON trial, which enrolled patients with Stage 4 CKD (eGFR 15 to 29 mL/min/1.73 m²) and type 2 diabetes. The overall increased risk for fluid overload and heart failure events with bardoxolone methyl appeared to be limited to the first three to four weeks after initiation of treatment. Elevated BNP and prior hospitalization for heart failure were identified as risk factors that contributed to increased risk for these events. The increased risk for these events from bardoxolone methyl treatment had not been observed in six previous CKD studies, which were conducted mostly in patients with Stage 3b CKD (eGFR of 30 to 44 mL/min/1.73 m²), patients with hepatic dysfunction, cancer patients, or healthy volunteers.

Review of admission notes and narrative descriptions for heart failure hospitalizations in BEACON indicates that heart failure in bardoxolone methyl-treated patients was often preceded by rapid fluid weight gain (several kilograms within the first weeks of treatment initiation) and was not associated with acute renal decompensation or acutely reduced left ventricular contractility. Available data from BEACON and other studies suggest that bardoxolone methyl treatment can differentially affect hemodynamic status according to the clinical condition of patients and likely promotes fluid retention in patients with more advanced renal dysfunction and other recognized risk factors associated with heart failure at baseline.

In a Phase 2 dose-ranging study of the efficacy and safety of bardoxolone methyl in patients with pulmonary hypertension (LARIAT), risk mitigation procedures were employed to reduce the potential for bardoxolone methyl-induced fluid overload; these procedures excluded patients with the identified risk factors and ensured close monitoring for fluid retention within the first month of treatment. To date, the risk for acute fluid overload AEs with bardoxolone methyl in late-stage CKD patients has not been observed in PH patients.

## 5.1.2.2. Transaminase and Gamma-glutamyl Transpeptidase (GGT) Elevations

In clinical studies of bardoxolone methyl, almost all patients had increases of transaminase enzymes above baseline upon initiation of treatment, which followed a consistent pattern. These increases were not associated with elevations in bilirubin or other signs of liver toxicity. In BEACON, fewer hepatobiliary SAEs were observed in the bardoxolone methyl arm than in the placebo arm. The elevations begin immediately after initiation of treatment or an increase in dose; they peak approximately two to four weeks later. In most patients, transaminase elevations were mild, but approximately 4% to 11% of patients experienced an elevation greater than 3X the ULN. The elevations resolved to levels less than the ULN in most all patients with elevations, within two weeks after peak values while patients continued taking study drug. Patients who experienced elevations to greater than 3X the ULN sometimes required additional time to resolve. While some patients have had elevations to above 3X the ULN, persistent

elevations to above 3X the ULN have not been observed, and the elevations did not recur once resolved, unless caused by other factors.

Bardoxolone methyl regulates GGT, a known Nrf2 target gene. In clinical studies, low level GGT elevations during treatment were common, mild, and typically lasted longer than ALT/AST elevations. Bilirubin levels in patients experiencing transaminase or GGT elevations due to treatment with bardoxolone methyl either remained at baseline levels or decreased. The ALT, AST, and GGT elevations were generally self-limiting in patients who continued treatment with study drug.

## 5.1.2.3. Muscle Spasms

Muscle spasm was the most frequently reported AE in clinical trials of bardoxolone methyl in patients with CKD who also had type 2 diabetes. The muscle spasms most often manifested in the first two months of treatment and resolved spontaneously or with empirical treatment. They occurred mostly at night, in the lower extremities, and were generally mild to moderate in severity. Muscle spasms have also been reported in bardoxolone methyl-treated PH patients but at lower incidences than that observed in prior CKD studies. Moreover, the incidence of muscle spasms is similar to that observed in placebo-treated PH patients. Muscle spasms may result from improved insulin sensitivity and glucose uptake in skeletal muscle cells. Increases in glucose uptake, as assessed by the hyperinsulinemic-euglycemic clamp procedure, were observed in response to bardoxolone methyl in a defined subset of patients enrolled in a Phase 2a study. To date, in those cases where serum creatinine kinase (CK) levels have been measured, no association has been observed between muscle spasms and elevated CK levels in patients treated with bardoxolone methyl. Clinical signs and laboratory findings associated with the reports of muscle spasms have not been consistent with muscle toxicity. Bardoxolone methyl subjects showed no increase in prominent laboratory findings associated with muscle toxicity, such as increased levels of serum markers, including creatinine, lactate dehydrogenase (LDH), BUN, uric acid, phosphorus, and potassium, which were monitored weekly during the first two months of a prior study (402-C-0804) when muscle spasms were most frequently reported.

Increases in the whole-body glucose disposal rate have been observed in mice treated with bardoxolone methyl, as well. Increased glucose uptake was observed in isolated calf muscles of the mice, but not in white adipose tissue (Saha, 2010).

#### 5.1.2.4. Weight Loss

Decreases in weight and reports of anorexia/decreased appetite have been observed following treatment with bardoxolone methyl in patients with CKD who also had type 2 diabetes. In studies of these patients, 17% of bardoxolone methyl patients reported AEs of weight decrease or decreased appetite (irrespective of relationship to treatment). Weight reduction was more pronounced in patients treated with bardoxolone methyl than in those given placebo.

Weight loss of approximately one kilogram per month was observed, with patients of higher body-mass index at baseline losing more weight (in absolute terms) than those of normal or moderately-elevated body-mass index.

Bardoxolone methyl-treated PH patients have also had decreases in weight, with mean weight decreases of approximately 3 kg versus placebo at Week 16. Weight loss in PH patients has not coincided with reports of decreased appetite or anorexia AEs.

## 5.1.2.5. Hypomagnesaemia

Hypomagnesaemia has not been reported in PH patients to date, but was reported as an AE for 15.5% of patients with CKD who also had type 2 diabetes who received bardoxolone methyl. The AE of hypomagnesaemia (of any reported relationship to study drug) was more frequently reported in bardoxolone methyl-treated patients than in patients given placebo. The investigators considered almost all reported events to be mild. Additionally, patients treated with bardoxolone methyl had a greater decrease from baseline in serum magnesium levels than patients given placebo; the decrease was evident within 4 weeks and attenuated after 8 weeks of starting therapy. In bardoxolone methyl clinical studies performed to date, a post-hoc analysis identified no correlation between hypomagnesaemia and either gastrointestinal AEs or cardiac AEs, including cardiac dysrhythmias and prolonged QTc. The 24-hour urine collections from the BEACON ambulatory blood pressure monitoring sub-study showed no increase in urinary magnesium levels, indicating that renal loss of magnesium did not account for the reductions in serum magnesium observed with bardoxolone methyl treatment in CKD patients. Notably, a thorough QT study that tested doses of bardoxolone methyl up to 80 mg, bardoxolone methyl showed no increase in the QT interval.

## 5.1.2.6. Increases in Urinary Protein

Increases in urinary albumin have been observed in some patients treated with bardoxolone methyl with chronic kidney disease and type 2 diabetes. The increases are likely due to bardoxolone methyl's pharmacological modulation of tubular protein reabsorption and have not been associated with interstitial fibrosis or injury. In preclinical studies, bardoxolone methyl has been shown to downregulate the primary proteins involved in protein reabsorption in the proximal tubules: the megalin-cubilin complex. Moreover, the magnitude of observed eGFR increases with bardoxolone methyl treatment is thought to reduce the residence time of protein in the proximal tubules, thereby reducing protein reuptake and increasing urinary protein levels. Therefore, increased eGFR, together with decreased megalin expression, is thought to result in decreased fractional absorption of albumin and increased urinary excretion of albumin. Consistent with bardoxolone methyl-mediated protection in preclinical models of protein-overload-induced nephropathy, these pharmacological effects are thought to reduce protein overload and secondary nephropathy caused by excessive albumin uptake and therefore are not associated with tissue injury and interstitial fibrosis.

## 6. STUDY OBJECTIVES AND ENDPOINTS

## 6.1. Primary Objectives

For patients within each cohort enrolled in this study, the primary objectives are as follows:

- To assess the change from baseline in estimated glomerular filtration rate (eGFR) in bardoxolone methyl-treated patients after 12 weeks of treatment.
- To assess the safety of bardoxolone methyl after 12 weeks of treatment.

## 6.2. Primary Efficacy Endpoint

Change from baseline in eGFR at Week 12.

# 6.4. Safety Endpoints

Frequency, intensity, and relationship to study drug of AEs and SAEs, and change from baseline in the following assessments: vital sign measurements, 12-lead ECGs, clinical laboratory measurements, and weight.

## 7. INVESTIGATIONAL PLAN

## 7.1. Overall Study Design

This multi-center, open-label Phase 2 trial will study the safety, tolerability, and efficacy of bardoxolone methyl in qualified patients with the following rare chronic kidney diseases: CKD associated with type 1 diabetes (T1D), IgA nephropathy (IgAN), focal segmental glomerulosclerosis (FSGS), and autosomal dominant polycystic kidney disease (ADPKD). Patients will be enrolled in disease specific cohorts within the trial, and effectiveness of bardoxolone methyl in treating CKD will be assessed separately by cohort for each rare CKD.

Patients will receive bardoxolone methyl throughout the study and the maximum bardoxolone methyl dose will be determined by baseline proteinuria status. Patients with macroalbuminuria  $(300 \text{ mg/g} < \text{ACR} \le 2500 \text{ mg/g})$  at the Screen B visit will account for up to approximately 50% of patients enrolled within each cohort. Patients with baseline ACR  $\le 300 \text{ mg/g}$  will be titrated to a maximum dose of 20 mg, and patients with baseline ACR  $\ge 300 \text{ mg/g}$  will be titrated to a maximum dose of 30 mg. Patients will start with once-daily dosing at 5 mg and will dose-escalate to 10 mg at Week 2, to 20 mg at Week 4, and then to 30 mg at Week 6 (only if baseline ACR  $\ge 300 \text{ mg/g}$ ) unless contraindicated clinically and approved by the medical monitor. Dose de-escalation is permitted during the study if indicated clinically, and subsequent dose re-escalation is also permitted to meet the dosing objective of the highest tolerated dose. Please refer to Section 7.3.1 for additional details on dose escalation and dose de-escalation.

All patients in the study will follow the same visit and assessment schedule. Following randomization on Day 1, patients will be scheduled to be assessed during treatment at Weeks 1, 2, 4, 6, 8, and 12, and by telephone contact on Days 3, 10, 21, 31, 38, and 45. Patients will also be scheduled to be assessed at an in person follow-up visit at Week 16, four weeks after the end of treatment.

#### 7.2. Number of Patients

Each cohort will enroll approximately 25 patients, for a total of approximately 100 patients in the trial.

## 7.3. Treatment Assignment and Rationale

All patients will receive bardoxolone methyl throughout the study. A dose-titration regimen is being utilized to allow for individual dose optimization based on tolerability and based on the anticipated maximally efficacious dose of bardoxolone methyl, which may vary based on a patient's proteinuria status at baseline. Based on results from prior trials in patients with type 2 diabetes and CKD, Reata has concluded that larger bardoxolone methyl doses may be required to have an optimal effect on eGFR in patients with macroalbuminuria. Specifically, eGFR improvements in patients with microalbuminuria were observed with a 20 mg bardoxolone methyl dose. In patients with macroalbuminuria, a 30 mg dose was required to produce a response that was similar to the patients with microalbuminuria treated at 20 mg. Consequently, the study includes dose titration up to a maximum dose of 20 mg for patients with ACR ≤ 300 mg/g and a maximum dose of 30 mg for patients with ACR > 300 mg/g, as described

below. From a safety perspective, the 30 mg dose may be associated with an increased incidence of nausea; however, the nausea experienced in previous trials is generally mild, transient, and clinically manageable.

#### 7.3.1. Dose Escalation

Patients will start with once-daily dosing of bardoxolone methyl at 5 mg and will dose-escalate to 10 mg at Week 2, to 20 mg at Week 4, and then to 30 mg at Week 6 (only if baseline ACR >300 mg/g) unless contraindicated clinically and approved by the medical monitor (Table 4). The dosing objective is to titrate patients to the maximum dose determined by baseline ACR, and maintain the maximum dose after initial dose-titration. The investigator should discuss any reason for not dose-escalating at Weeks 2 and 4 with the medical monitor. Dose escalation at subsequent visits is permitted to meet the dosing objective.

Table 4: Bardoxolone Methyl Dose by Study Visit and Albuminuria Status

Baseline ACR	Day 1	Week 2	Week 4	Week 6 to Week 12		
ACR ≤ 300 mg/g	5 mg	10 mg	20 mg	20 mg		
$300 \text{ mg/g} < ACR \le 2500 \text{ mg/g}$	5 mg	10 mg	20 mg	30 mg		

#### 7.3.2. Dose De-Escalation and Re-Escalation

The investigator may choose to decrease the patient's dose to the prior dose (e.g., 20 mg to 10 mg, or 10 mg to 5 mg), if clinically indicated. Dose de-escalation may occur more than once, but the minimum dose permitted is 5 mg. Reasons for dose de-escalation should be discussed with the medical monitor prior to changing dose and must be documented. After dose de-escalation, patients should return for an unscheduled office visit within 4 weeks (± 3 days) to collect clinical chemistry and to perform the assessments detailed in Section 9.7.

Once a patient's dose has been reduced, dose re-escalation back to a higher dose is permitted to meet the dosing objective. However, patients who dose re-escalate must have a telephone call 1 week after dose escalation and an unscheduled office visit 2 weeks (± 3 days) after dose escalation to collect clinical chemistry, BNP, and NT-proBNP. Unscheduled visits due to dose escalation should also include assessments detailed in Section 9.7.

## 7.4. Criteria for Study Termination

Although the Sponsor intends to complete the study, the Sponsor reserves the right to discontinue a cohort or the study at any time for clinical or administrative reasons, or if required by regulatory agencies. If the Sponsor discontinues the study, all study drug will be discontinued and the investigator will be responsible for securing any alternative therapy to be administered, as appropriate.

#### 7.5. Schedule of Assessments

Table 5 lists the overall schedule of assessments for the study.

Table 5: Schedule of Assessments

Assessment	Screen A a	Screen B b	Day 1°	Wk 1 (Phone) Day 3±2	Wk 1 Day 7±3	Wk 2 (Phone) Day 10±2	Wk 2 Day 14±3	Wk 3 (Phone) Day 21±2	Wk 4 Day 28±3	Wk 4 (Phone) Day 31±2	Wk 5 (Phone) Day 38±2	Wk 6 Day 42±3	Wk 7 (Phone) Day 45±2	Wk 8 Day 56±3	Wk 12 or EoT d Day 84±3	Wk 16 or F/U Day 112±3
Informed consent	X															
Inclusion/ exclusion	X		Χ°													
Demographics and baseline disease characteristics	X															
Concomitant medications	X	X	X	X	X	X	X	X	X	X	X	X	X	X	X	X
Medical history	X															
Height	X															
Weight in clinic/BMI	X		X		X		X		X			X		X	X	X
Weight at home			X	X	X	X	X	X	X	X	X	X	X	X	X	
Dispense weight diary			X				X		X			X		X		
Collect/review weight diary				X	X	X	X	X	X	X	X	X	X	X	X	
ECG	X														X	X
Echocardiogram f	X															
Vital sign measurements	X		X		X		X		X			X		X	X	X
Physical exam	X		X		X		X		X			X		X	X	X
Pregnancy test for WOCBPs	X	X	X						X					X	X	X
Study drug administration									Х	ζ			_			
Dispense study drug			X				X		X			X		X		
Collect study drug							X		X			X		X	X	
Telephone contact				X		X		X		X	X		X			
Adverse event collection			Xh	X	X	X	X	X	X	X	X	X	X	X	X	X
Kidney biopsyi	X															
Fasting C-peptide level j	X															
Genetic testing k	X															
Clinical chemistry (incl. eGFR)	X	X	X		X		X		X			X		X	X	X
BNP and NT-proBNP	X		X		X		X		X			X		X	X	X
IGF-1 and serum ketones	X		X		X		X		X			X		X	X	X
Hematology	X		X				X		X			X		X	X	X
Urinalysis and microscopy	X		X				X		X			X		X	X	X
Urine collection for ACR1		X	X						X					X	X	X
															X	X
															X	X
Virus serology	X															
PK samples m															X	

Protocol 402-C-1702 Reata Pharmaceuticals, Inc. Confidential

- a Total Screening period should not exceed 6 months.
- b Screen B visit should be no more than 30 days prior to Day 1.
- c Day 1 is the day of administration of the first dose. On Day 1, all procedures should be performed before study drug administration.
- d Patients who terminate from the study prior to the Week 12 study visit should be brought back to the clinic as soon as possible for early termination assessments (i.e., end-of-treatment visit) as well as a follow-up visit 4 weeks later.
- e Screening eligibility procedures do not need to be repeated on Day 1; however, a review of any changes in eligibility criteria should be evaluated prior to Day 1 procedures, and a urine pregnancy test should be performed for WOCBP.
- f An echocardiogram performed at the Screen A visit or within 6 months prior to Day 1 may be used to determine eligibility.
- g A serum pregnancy test will be performed at the Screen A visit for WOCBP or at any point in time if a pregnancy is suspected. All other pregnancy assessments will be urine pregnancy tests.
- h AE assessments on Day 1 should be performed following study drug administration.
- Only patients enrolling in the IgA nephropathy cohort or the FSGS cohort are required to have a kidney biopsy. Patients with definitive diagnosis of IgA nephropathy or FSGS from previous biopsy will not have a kidney biopsy as part of the study, but must provide diagnosis documentation from previous kidney biopsy for eligibility.
- j Only patients enrolling in the T1D cohort are required to have fasting C-peptide levels assessed. Patients should be instructed to fast prior to study visit.
- k Only patients enrolling in the ADPKD disease cohort are required to have genetic testing. Patients with confirmed PKD1 mutations from previous genetic testing will not have genetic testing performed as part of the study, but must provide documentation of genetic mutation for eligibility.
- Albumin to creatinine ratio will be measured by first morning void spot urine collection. Appropriate containers for the collection will be provided to the patient at the visit prior to collection.
- mPatients must be instructed to not take their study drug prior to coming to the clinic for visits when PK samples will be collected. Patients must administer the study drug dose in the clinic on PK sample collection visits after the 0 hour PK blood sample is collected. Patients will have blood samples for PK analysis drawn just prior to (0 hour) and after (2 and 4 hours) dose administration.

Abbreviations: EoT= end-of-treatment; ECG = electrocardiogram, F/U = follow-up; PK = pharmacokinetic, WOCBP = women of child-bearing potential

## 8. SELECTION AND WITHDRAWAL OF PATIENTS

#### 8.1. Patient Inclusion Criteria

Diagnosis and main criteria for inclusion:

- Male and female patients 18 ≤ age ≤ 60 upon study consent;
- Screening eGFR (average of Screen A and Screen B eGFR values) ≥ 30 and ≤ 90 mL/min/1.73 m². The two eGFR values collected at Screen A and Screen B visits used to determine eligibility must have a percent difference ≤ 25%;
- Albumin to creatinine ratio (ACR) ≤ 2500 mg/g at Screen B visit;
- 4. If receiving an angiotensin converting enzyme (ACE) inhibitor and/or an angiotensin II receptor blocker (ARB), patients should be prescribed the maximally tolerated labeled daily dose (MTLDD), as defined in Section 9.1.7, for at least 6 weeks prior to the Screen A visit. The dosage of ACE inhibitor and/or ARB should remain the same throughout the remainder of the study (i.e., no change in dosage or medication), and any potential changes should be discussed with the medical monitor. Patients not taking an ACE inhibitor and/or ARB because of a medical contraindication may be eligible if they have discontinued treatment at least 8 weeks prior to the Screen A visit (these patients must be discussed with the medical monitor prior to enrollment);
- For patients enrolling in T1D Cohort:
  - Diagnosis of type 1 diabetes confirmed by fasting C-peptide level. Diagnosis must have been made ≤ 35 years of age;
  - Prescribed stable dose of insulin to maintain adequate glucose control for at least 6 months prior to the Screen A visit;
- For patients enrolling in IgAN Cohort:
  - Biopsy-confirmed IgA nephropathy;
- For patients enrolling in FSGS Cohort:
  - Biopsy-confirmed FSGS that is not due to known secondary causes including morbid obesity, decreased renal mass, viral infections, drug-induced nephrotoxicity, or prior history of vasculitis;
- For patients enrolling in ADPKD Cohort:
  - Genetic confirmation of PKD1 mutation;
- Adequate bone marrow reserve and organ function at the Screen A visit as follows:
  - Hematologic: Absolute neutrophil count > 1.5 x 10^3/L, platelets > 100 x 10^3/L, hemoglobin (Hgb) ≥ 9 g/dL;
  - b. Hepatic: Total bilirubin (TBL) ≤ 1.5X the upper limit of normal (ULN), alanine aminotransferase (ALT) and aspartate aminotransferase (AST) ≤ 1.5X ULN;
- Able to swallow capsules;

- Willing and able to comply with scheduled visits, treatment plan, laboratory tests, and other study procedures;
- 12. Evidence of a personally signed and dated informed consent document indicating that the patient has been informed of all pertinent aspects of the study prior to initiation of any patient-mandated procedures.

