9.3. Demographics and Baseline Characteristics

Demographics and baseline characteristics will be summarized by rare CKD cohort for the safety analysis set. Demographic characteristics will include age, gender, race, and ethnicity. Baseline ACR will be summarized by baseline ACR values, not the stratification cohort to which a patient was randomized. The baseline characteristics include:

- Baseline weight,
- Height,
- Body mass index (BMI), and BMI category: < 30 , ≥ 30 ,
- Baseline values of eGFR, baseline CKD stage (Stage 3: eGFR 30 to < 60 ; Stage 2: eGFR ≥ 60 to < 90 ; Stage 1: eGFR ≥ 90),
- Baseline serum creatinine,
- Baseline ACR,
- Baseline ACR status (ACR ≤ 300 mg/g; 300 mg/g $<$ ACR ≤ 1000 mg/g; ACR $>$ 1000 mg/g),
- Age of the diagnosis (T1D cohort only)
- C-peptide level (T1D cohort only),
- Prescribed a stable dose of insulin (T1D cohort only), and

- Baseline Angiotensin converting enzyme (ACE)-inhibitor and Angiotensin II receptor blocker (ARB) use:
 - Only ACEi treatment;
 - Only ARB treatment;
 - ACEi and ARB treatment
 - No ACEi or ARB treatment.

The above information will be listed by patient.

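### The T1D cohort's entry criteria do not require evidence of kidney disease, so patients with eGFR 60-90 and normal ACR can be analysed as having CKD associated with T1D

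*Protocol*

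**What the plan says.** Protocol Section 7.1 states the aim by cohort: "effectiveness of bardoxolone methyl in treating CKD will be assessed separately by cohort for each rare CKD". SAP Section 1 defines the T1D label as chronic kidney disease associated with type 1 diabetes.

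The entry rules are in Protocol Section 8.1, and the synopsis has the same T1D, eGFR and ACR criteria.

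- T1D cohort, diagnosis: "Diagnosis of type 1 diabetes confirmed by fasting C-peptide level. Diagnosis must have been made ≤ 35 years of age".
- T1D cohort, treatment: "Prescribed stable dose of insulin to maintain adequate glucose control for at least 6 months prior to the Screen A visit".
- All cohorts, eGFR: "Screening eGFR (average of Screen A and Screen B eGFR values) ≥ 30 and ≤ 90 mL/min/1.73 m²".
- All cohorts, ACR: "Albumin to creatinine ratio (ACR) ≤ 2500 mg/g at Screen B visit".
- IgAN and FSGS need biopsy confirmation; ADPKD needs a confirmed PKD1 mutation.

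Protocol Section 9.10.2 makes the listed inclusion and exclusion criteria decisive for entry. Under Section 7.1, macroalbuminuric patients "will account for up to approximately 50% of patients enrolled within each cohort".

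SAP Section 9.3 stages CKD at baseline by eGFR alone, with 60 to below 90 called Stage 2. Its lowest ACR category is 300 mg/g or less. SAP Section 11.1.1 tests the mean Week 12 change in eGFR against zero, with no control arm.

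**The concern.** T1D is the only cohort whose qualifying diagnosis is not a kidney disease. Diabetes and insulin use say nothing about the kidney, and the common criteria only partly make up for it. A patient with neither reduced eGFR nor albuminuria can enter and be counted as a CKD patient.

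What is at stake is interpretation. The cohort is meant to show whether the drug is effective in treating CKD in T1D, and patients without CKD do not inform that question. With about 25 patients and one arm, a few of them form a visible part of the result. The planned tables would not show how many there are, because normal ACR is merged with microalbuminuria and eGFR 60 to below 90 is given a CKD stage whatever the ACR.

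The dose rationale in Protocol Section 7.3 has a related gap. For the lower ACR group it cites patients with microalbuminuria ("eGFR improvements in patients with microalbuminuria were observed with a 20 mg bardoxolone methyl dose"), while the group itself has no lower ACR bound.

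**Working it through.** **1. The plan's own figure.** Protocol Section 12.1 and SAP Section 6 give about 80% power with 25 patients per cohort. The effect size and SD are not visible, so this cannot be reproduced. Inverting it (one-sample t-test, n = 25, two-sided 0.05) gives a standardized change of 0.584. Nothing below depends on it.

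**2. Can a patient without evidence of kidney disease pass?** The CKD-EPI equation in SAP Section 7.1.3, without the race factor, for a man aged 45 with creatinine 1.1 mg/dL:

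141 × (1.1/0.9)^-1.209 × 0.993^45 = 80.6 mL/min/1.73 m²

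A woman aged 40 with creatinine 0.9 mg/dL gives 80.0. Both lie within 30-90. An ACR of 5 mg/g is below 2500. With type 1 diabetes diagnosed by age 35 and stable insulin, both meet every kidney-related inclusion criterion. No exclusion in Section 8.2 asks for albuminuria, a prior CKD diagnosis or a documented decline.

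**3. Which patients are affected?**

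| Screening eGFR | ACR < 30 mg/g | ACR ≥ 30 mg/g |
|---|---|---|
| 30 to < 60 | reduced function shown | reduced function and albuminuria shown |
| 60 to 90 | **neither shown** | albuminuria shown |

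Only one cell is open. The cut-points 60 and 30 mg/g are used here as an assumption. SAP Section 9.3 uses 60 for staging and Protocol Section 9.1.7 uses 30 mg/g for blood pressure targets, but neither document defines CKD by them.

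**4. How many?** With macroalbuminuria capped at about 50%, about 0.5 × 25 = 12.5 patients or more fall in the ACR ≤ 300 mg/g group. That is the size of the group without a floor, not the number without CKD. The documents give no ACR distribution within it.

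**5. Can the effect on the mean be sized?** Protocol Table 3 gives a gain of 14.7 in pulmonary hypertension at baseline eGFR 82, and 6.5 in an 85-day study in T2D and CKD. If a share p of the cohort lacks CKD, the shift is p × (gain without CKD − gain with CKD). At an assumed p = 20%:

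- With 14.7 and 6.5: 0.20 × 8.2 = 1.6.
- If gain instead scales with baseline eGFR: 14.7/82 = 18%, and 7.4/32.4 = 23% for the Phase 2b T2D study in Section 5.1.1. CKD patients at an assumed average eGFR of 60 would gain about 10.8 to 13.7, so the shift is 0.20 × (14.7 − 10.8) = 0.8 down to 0.20 × (14.7 − 13.7) = 0.2.

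The answer runs from 0.2 to 1.6 at one assumed share, depending on an assumption the documents do not settle.

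**6. Does the model remove the problem?** SAP Section 11.1.2 adjusts for baseline eGFR and log ACR. In a single-arm model the LS means are by default evaluated at the cohort's own covariate means, so adjustment does not undo who was enrolled.

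**The case against.** The strongest case on the other side has five parts.

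- **The stated population is CKD associated with T1D.** True of the design section, but entry is decided by the listed criteria and none of them requires CKD. Protocol Section 5 describes CKD as decreased kidney function without a threshold.
- **Other criteria narrow the pool.** Inclusion criterion 4 and Section 9.1.7 expect maximally tolerated ACE inhibitor or ARB dosing, and investigators may exclude anyone they judge unsuitable. This probably reduces the number of such patients. Neither provision shows kidney disease, and the second is discretionary.
- **The patients can be found.** SAP Section 9.3 lists eGFR and ACR by patient, and up to five years of historical creatinine are collected. So they are identifiable in listings, but no visible table or analysis separates them.
- **The thresholds are not the documents' definition of CKD.** This stands, and the fix leaves the definition to the sponsor.
- **A larger gain at higher eGFR is not a T1D problem.** This stands too. A reader might infer from Table 3 that patients without CKD would inflate the T1D result by a calculable amount. The documents do not support that. The 14.7 is placebo-corrected, at 16 weeks and in another disease; the 6.5 is an uncontrolled change from baseline. The contrast is also confounded with baseline eGFR: a T1D patient at eGFR 82 and ACR 30 mg/g would satisfy the proposed criterion with perhaps much the same gain, as might an IgAN, FSGS or ADPKD patient at eGFR 82.

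**Conclusion.** The eligibility gap is real and follows from the criteria alone. The T1D cohort can include patients with eGFR 60-90 and normal ACR who show no evidence of kidney disease, so its Week 12 estimate may not answer the CKD question it is meant to answer.

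Its size is unknown. The share of such patients could be nil, and no figure for a shift in the cohort mean should be quoted. Table 3 suggests larger absolute gains at higher baseline eGFR, but this applies to every cohort and is not specific to absence of CKD.

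A reader might also infer a higher false-positive rate. That does not follow: the null is zero mean change in whoever is enrolled, and its nominal type I error is unaffected.

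The conclusion assumes that CKD means something like eGFR below 60 or ACR of at least 30 mg/g, and that no redacted analysis already makes the split. This is a cheap improvement to a small Phase 2 cohort, not a flaw in the test.

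**What to change.** 1. **Protocol Sections 2 and 8.1, T1D cohort.** Add a requirement for evidence of CKD, for example screening eGFR < 60 mL/min/1.73 m², or Screen B ACR ≥ 30 mg/g, or documented diabetic nephropathy. The sponsor should confirm the definition. Both laboratory values are already measured at screening, and medical history is taken at Screen A.
2. **SAP Section 11.** Report the T1D Week 12 estimate with and without patients who lack this evidence. This needs no new data and still works if enrolment is complete.
3. **SAP Section 9.3.** Split the ACR ≤ 300 mg/g category at 30 mg/g in the T1D baseline table.

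The cost is slightly slower T1D recruitment, one supplementary analysis and one extra table row. The restricted estimate is also less precise: if 5 of 25 patients were left out (an assumed number), the standard error would rise by about √(25/20) − 1 = 12% at the same SD.
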